Given most studies regarding the effectiveness and safety of the early follicular phase full-dose down-regulation protocol are retrospective studies, the results may be biased by several confounding factors. Therefore, we would like to conduct a multicenter, randomized controlled trial to compare the pregnancy outcome and safety between the early follicular phase full-dose down-regulation COH protocol and the luteal phase down-regulation protocol.

Methods/Design

We will perform the multicenter, randomized controlled trial in 14 reproductive medicine centers all over mainland China. Included patients will be distributed in a 1:1 ratio to the intervention (early follicular phase full-dose down-regulation) group and the control (mid-luteal phase down-regulation) group. Their live birth rate of fresh embryo transfer and other secondary outcomes will be compared. This study has been approved by the institutional review boards at all study sites. Each participant will sign the consent form before inclusion. Reporting of the study results will follow the 2010 CONSORT statement [11].

Inclusion criteria

The following are the inclusion criteria for this study:

1. Women aged between 20 to 38 years old and with a history of infertility (fail to get pregnant after over one year's regular, unprotected sex), who receive IVF/ICSI for one of the following reasons:
 - ① Tubal factor: e.g. peritubal adhesions, tubal obstruction, etc.. Patients with hydrosalpinx can be enrolled after salpingectomy or tubal ligation;
 - ② Male factor: e.g. oligospermia, asthenozoospermia, teratozoospermia, etc.;
 - ③ Unexplained infertility: patients with a history of infertility more than 1 year but with no specific cause for infertility (ovulation, tubal, endometrial and male factor), or still not get pregnant after the above-mentioned causes being removed.
2. Women with a normal ovarian reserve according to: ① basal steroid hormone on day 2-4 of menstrual cycle: basal FSH≤10mIU/ml, estradiol (E2) <50pg/ml; ② anti-Müllerian hormone (AMH)≥1.1ng/ml; ③ antral follicle count (AFC) ≥7;
3. Women who start their first IVF/ICSI cycle;
4. Women who met the above-mentioned criteria and have given the informed consent.

Exclusion criteria

1. Women with a negative reproductive history, including a history of:
 - ① recurrent miscarriage: women with twice and more than twice spontaneous miscarriage, missed abortion, biochemical pregnancies, etc.;

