 - ② fetal malformation or chromosomal abnormalities;

- ③ intrauterine death.
- 2. Women with a history of one side adnexectomy;
- 3. Women with a poor ovarian response or diminished ovarian reserve (based on Bologna' criteria);
- 4. Women with ovulation dysfunction;
- 5. Women with PCOS (based on Rotterdam's criteria);
- 6. Women with endometriosis;
- 7. Women with the following uterine abnormalities: uterine malformation (unicornuate uterus, uterus bicornis, uterus duplex, mediastinum uterus), adenomyosis, submucosa myoma, intrauterine adhesion;
- 8. Chromosomal abnormality for either or both of the couple;
- 9. Women with contraindications for ART or pregnancy: uncontrolled diabetes mellitus, cardiac disease, undiagnosed liver and/or renal function, vaginal bleeding, suspected or a past history of cervical cancer, endometrial cancer, breast cancer, and a history of deep venous thrombosis, pulmonary embolism, stroke, etc.;
- 10. Women who are enrolled in other clinical trials.

Randomization

After the evaluation, patients met the eligible criteria will be informed, sign the consent form and be included in this study. We will randomly assign women (1:1) to the two groups, using a central randomization system with block sizes of 4 to 6 (changing constantly) and setting hospital as a stratification factor. The researchers (physicians, nurses and embryologists) and patients are not blinded due to the nature of both interventions while the data analysts are blinded.

Interventions

Pituitary down-regulation and controlled ovarian hyperstimulation(COH)

1. *Pituitary down-regulation and starting dose determination*

After inclusion and randomization, qualified participants will be in either intervention or control group and receive one of the following treatments:

1) *Intervention group* (early follicular phase full-dose down-regulation group)

Patients have an injection of 3.75mg long-acting triptorelin acetate (Dipherelin®, IPSEN, France) on the 1st-4th day of menstrual cycle and receive the endocrinology and ultrasound examinations 28-42 days thereafter. If complete pituitary down-regulation is achieved (endometrial thickness≤5mm, basal FSH≤5mIU/mL, LH≤5mIU/mL, E2≤50pg/mL) and the diameter of follicles between 4-6mm under ultrasound, a supplementation of recombinant FSH (Gonal-F®, Merck, Switzerland) will be given according to the participants' BMI (18≤BMI≤22, starting dose 112.5IU/d; 22<BMI≤25, starting dose 150IU/d.

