2) *Control group* (luteal phase long down-regulation group)

Patients have an injection of short-acting triptorelin acetate (Decapeptyl®, Ferring, Germany) 0.1mg every day, 10-12 days before the menstruation and receive the endocrinology and ultrasound examinations 14-21 days thereafter. If complete pituitary down-regulation is achieved (endometrial thickness≤5mm, basal FSH≤5mIU/mL, LH≤5mIU/mL, E2≤50pg/mL) and the diameter of follicles between 4-6mm under ultrasound,

a supplementation of recombinant FSH (Gonal-F®, Merck, Switzerland) will be given according to the participants' BMI ($18 \leq \text{BMI} \leq 22$, starting dose 112.5IU/d; $22 < \text{BMI} \leq 25$, starting dose 150IU/d).

2. *Ovarian response monitoring and gonadotropin dose adjustment:* 4 days after the daily injection of rFSH, the physician will perform ultrasound to monitor the follicular growth, measure the serum hormone level and adjust the dose of exogenous gonadotropins accordingly.

Trigger and oocyte retrieval

1. *hCG trigger for final oocyte maturation:* When the desired follicle size is reached (at least one follicle ≥ 19 mm or two follicles ≥ 18 mm or three follicles ≥ 17 mm), 250 μ g recombinant human chorionic gonadotropin (HCG) (Luveris®, Merck, Switzerland) will be administered subcutaneously.
2. *Oocyte retrieval:* Oocyte retrieval will be performed transvaginally 36-38 hours after pre-ovulatory hCG injection under ultrasound monitoring.
3. *In vitro fertilization and embryo culture:* Oocyte retrieved will be cultured in vitro for 3-6h before being fertilized via IVF or ICSI. Two top-quality Day 3 cleavage embryos will be transferred 72h after retrieval. If more than 15 oocytes are retrieved, the participant should receive ultrasound examination on the day of embryo transfer. For those complaining abdominal or stomach distension, with an ovary ≥ 7 cm in diameter, estradiol ≥ 4500 pg/ml, there is a high risk of developing moderate or severe OHSS, and all the embryos should be frozen.

Embryo transfer and luteal phase support

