For those not receiving a fresh embryo transfer (e.g. due to OHSS), and those not achieving live birth and with surplus cryopreserved embryos, the outcome of frozen-thawed embryo transfer cycles will be followed up and recorded as well.

Outcome measurements

Primary outcome

The primary outcome of this study is live birth rate per transferred cycle, defined as delivery of any viable infant ≥ 28 gestational weeks divided by all transferred cycles.

Secondary outcomes

Secondary effectiveness endpoints will include implantation rate, biochemical pregnancy, clinical pregnancy and ongoing pregnancy. *Biochemical pregnancy* will be achieved if serum β -hCG ≥ 10 U/L. *Clinical pregnancy* is defined as the presence of an intrauterine gestational sac 28 ± 4 days after embryo transfer. Ongoing pregnancy is defined as a viable pregnancy at 10-12 gestational week. The safety endpoints will include moderate and severe OHSS, pregnancy loss, pregnancy complications, neonatal birth weight and adverse fetal outcomes (e.g. malformation, intrauterine fetal death, etc.)

Statistical analysis

Sample size and power calculation

Sample size will be calculated based on superiority test. The significance level will be set at $\alpha = 0.05$ and the statistical power will be set as $1 - \beta = 0.80$. The reported live birth rate is about 30%, while the live birth rate of the prolonged protocol is predicted to be around 40% based on previous retrospective studies. We set the delta value as 6%, and the ratio between groups will be 1:1; therefore, the sample size of each group is 851. Taking into consideration a drop rate of 10%, we expect to ultimately have a total of 1892 enrollees, with 946 participants in each group.

Statistical analysis method

1. Statistical description: We will adopt descriptive statistical analysis to summarize the participants' demographic characteristics, physical examination, laboratory tests, other health information and the outcome indicators. The continuous variables will be described with means and standard deviation (or median and interquartile range), while the categorical variable will be described with frequency and percentage. The proportion of drop-off cases will be calculated and analyzed.

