2. Comparable analysis It will be used to compare the demographic and other baseline characteristics to make sure the comparability of the two groups. If the continuous variables follow the normal distribution, t test will be performed; if not, the rank sum

test or a normal transformation will be performed. For the categorical variables, chi-square test or Fisher's exact test will be performed.

3. Statistical analysis for the outcome measures Between-group differences for categorical and continuous outcome variables will be assessed by logistic regression and linear regression, respectively.
4. Safety analysis: Adverse events and reaction will be listed and analyzed using the chi-square test.
5. The analysis for the primary outcome and important outcome measurements will be based on both the intention-to-treat analysis and per-protocol analysis. The results of these two analyses will be compared in the final analysis.

Reference

- [1] The United Kingdom national data. Human Fertility and Embryology Authority. 2015
- [2] The United States national assisted reproductive technology(ART) data. Centers for Disease Control and Prevention.2015
- [3] Chinese Reproductive Medicine Society national assisted reproductive technology (ART) data. 2015
- [4] L Hu, Y Sun. The impact of various controlled ovarian hyperstimulation (COS) protocols on the outcome of in vitro fertilization and embryo transfer (IVF-ET). *Journal of Practical Obstetrics and Gynecology*. 2014;30(10):723-725.
- [5] Y Hu, T Ding, Y Zhao, Q Wu. The comparison of the birth outcome of in vitro fertilization and embryo transfer (IVF-ET) after two different down-regulation protocols. *Maternal and Child Health Care of China*.2017;32(4):808-810.
- [6] D Xu, Q Wu. The comparison of the application of ultra-long down-regulation protocol and antagonist protocol in in vitro fertilization and embryo transfer (IVF-ET). *Jiangxi Medical Journal*. 2015;50(1):13-15.
- [7] Q Su, Q Wu, L Tian, Y Li. The clinical analysis of different controlled ovarian hyperstimulation (COS) protocols in in vitro fertilization and embryo transfer (IVF-ET). *Jiangxi Medical Journal*. 2014;49(8):723-725.
- [8] Y Li, Q Wu, Y Yi. The impact of the follicular phase ultra-long long down-regulation protocol on PCOS patients' outcome after in vitro fertilization and embryo transfer (IVF-ET). *Jiangxi Medical Journal*. 2014;49(2):117-120.

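### Randomisation is stratified by hospital but the outcome regressions name no hospital term; adding it to the main models brings a small gain in power and keeps test size near 5%

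*Combined protocol and SAP*

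**What the plan says.** The Methods/Design section states: "We will perform the multicenter, randomized controlled trial in 14 reproductive medicine centers all over mainland China". Under Randomization, women are allocated 1:1 "using a central randomization system with block sizes of 4 to 6 (changing constantly) and setting hospital as a stratification factor".

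Statistical analysis method, item 3, is the whole specification of the outcome model: "Between-group differences for categorical and continuous outcome variables will be assessed by logistic regression and linear regression, respectively". It lists no covariates. Items 1, 2 and 5 add no hospital term. Item 4 handles safety separately: "Adverse events and reaction will be listed and analyzed using the chi-square test". Item 5 applies to the main outcomes: "The analysis for the primary outcome and important outcome measurements will be based on both the intention-to-treat analysis and per-protocol analysis".

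Two further passages matter. Under Primary outcome: "The primary outcome of this study is live birth rate per transferred cycle". And under Trigger and oocyte retrieval, item 3, some women leave the fresh-transfer denominator after randomisation because "there is a high risk of developing moderate or severe OHSS, and all the embryos should be frozen".

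**The concern.** Blocking within hospital makes the arms nearly equal in each hospital, so differences between hospitals largely cancel out of the comparison. A regression without hospital does not use this. Its standard error still counts the between-hospital variation, so it is slightly too large and the test rejects a true null hypothesis less often than 5%.

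Item 3 also leaves open which odds ratio will be reported. The odds ratios with and without hospital are different quantities (non-collapsibility, not bias), and item 3 as written allows either. The choice should be fixed before the data are seen.

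Some hospital variation is plausible from the protocol itself, which leaves certain treatment adjustments to the physicians at each site. The documents do not say how large it is.

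**Working it through.** **Inputs from the documents.** 14 hospitals; 1:1 allocation; control rate 30%; predicted intervention rate 40% ("the live birth rate of the prolonged protocol is predicted to be around 40% based on previous retrospective studies"); delta 6%; alpha 0.05; 851 per arm; 10% dropout.

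**Assumptions.** The test is two-sided (the plan does not say). Hospitals are of equal size. Hospital effects are normal on the log-odds scale with SD 0.2 / 0.3 / 0.5, which corresponds to control-arm hospital rates of about 22–39 / 19–43 / 13–52% (central 95%). The 36% used below appears nowhere in the documents. It is 30% plus the 6% delta, read as an effect size; the plan does not say whether delta is an effect or a superiority margin.

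**The plan's own figures.** The dropout step reproduces: 851 / 0.9 = 945.6, so 946 per arm and 1892 in total. The 851 does not follow from the stated rates: at 80% power, two-sided, 30% v 40% needs 356 per arm and 30% v 36% needs 963. That is a separate matter; 851 is used here only as the planned number analysed.

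**Step 1, variance ratio.** Let r be the mean within-hospital binomial variance divided by the total binomial variance, with intercepts solved so that the overall rates are kept.

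| SD | 0.2 | 0.3 | 0.5 |
|---|---|---|---|
| r, 30% v 30% | 0.992 | 0.982 | 0.952 |
| r, 30% v 36% | 0.991 | 0.981 | 0.950 |
| r, 30% v 40% | 0.991 | 0.980 | 0.949 |

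**Step 2, test size without hospital.** Size = 2 × [1 − Φ(1.96/√r)], using the 30% v 30% ratio: 4.91 / 4.79 / 4.45%. A simulation of 40,000 trials per setting gave 4.91 / 4.80 / 4.44% without hospital and 5.09 / 5.08 / 5.12% with 14 hospital levels (Monte Carlo SE 0.11 points).

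**Step 3, power.** With SE = √{[p₁(1−p₁) + p₂(1−p₂)]/851}:
- without hospital: Φ[(δ/SE − 1.96)/√r]
- with hospital: Φ[δ/(SE√r) − 1.96]

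At 30% v 36%, SE = √[(0.21 + 0.2304)/851] = 0.02275 and δ/SE = 2.637. For SD 0.5, √r = 0.974. Without hospital, Φ(0.677/0.974) = Φ(0.695) = 75.7%. With hospital, Φ(2.707 − 1.96) = Φ(0.747) = 77.2%.

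At 30% v 40%, SE = √[(0.21 + 0.24)/851] = 0.02300 and δ/SE = 4.349.

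| SD | 0.2 | 0.3 | 0.5 |
|---|---|---|---|
| 30% v 36%, without | 75.2% | 75.3% | 75.7% |
| 30% v 36%, with | 75.5% | 75.9% | 77.2% |
| Gain (points) | 0.3 | 0.6 | 1.6 |
| 30% v 40%, without | 99.2% | 99.2% | 99.3% |
| Gain (points) | 0.02 | 0.04 | 0.10 |

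Simulated gains at 30% v 36% were 0.4 / 0.8 / 1.7 points. About 0.3 of that also appears at SD 0 and reflects a slightly liberal 14-level fit, so the closed-form gains are the ones to quote. A separate simulation with unequal hospitals agreed in direction and size: test size 4.8 / 4.7 / 4.5% without hospital and gains of 0.6 / 0.9 / 1.8 points.

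**Step 4, effect scale, at 30% v 36%.** The risk-difference SE falls from 2.275 to 2.265 / 2.253 / 2.217 points. The log-odds SE rises from 0.1034 to 0.1039 / 0.1044 / 0.1062, while the odds ratio moves from 1.31 to 1.32 / 1.32 / 1.33.

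**Step 5, transferred cycles.** Transfer fractions are assumed; 946 randomised per arm; 30,000 simulated trials each.
- Transfer 90% in both arms: size without hospital 4.7 / 4.8 / 4.4%.
- 80% control v 95% intervention in every hospital: 4.9 / 4.7 / 4.7%.
- 80% v 95%, with the control fraction varying between hospitals (log-odds SD 0.5) and perfectly aligned with the hospital's live birth rate: 5.2 / 5.6 / 6.8%, from a spurious null difference of 0.4 / 0.6 / 0.9 points.
- 70% v 95%, with hospital variation in transfer at SD 1.0: 5.1–5.5%.

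With hospital in the model, size is 4.9–5.2% throughout, and the spurious difference in the aligned case is 0.0.

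**Step 6, rare outcomes.** At an assumed 1% event rate, 1892/14 ≈ 135 women per hospital gives a chance of no events of 0.99^135 ≈ 0.26, so about 14 × 0.26 ≈ 4 hospitals have none. Their terms cannot be estimated in ordinary logistic regression. In simulation the arm comparison was not harmed (size 4.0% either way), but nothing was gained.

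**The case against.** The strongest objection is materiality. At the only two rates that the plan states, power is already about 99% and the gain is 0.10 points or less. The 1.6-point gain needs both the 36% reading of delta and hospital rates spread over about 13–52%, while the narrow eligibility criteria limit differences in patient mix (though not in laboratory practice). Item 3 names a model family and does not rule covariates out. All of this stands, and it keeps the point minor.

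A reader might infer that omitting hospital invalidates the primary test or inflates false positives. The documents do not support that: among randomised women the error is towards conservatism. Size above 5% appeared only under strong, undocumented assumptions about transfer. Nor can it be said that size always falls below 5%, because those same cases reverse it.

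A reader might also infer that adjustment narrows every interval, or that it costs nothing. On the log-odds scale the SE rises and the odds ratio becomes conditional on hospital. Nor does a 14-level term suit every endpoint, as the rare-event count shows.

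Finally, a hospital term should not be taken as a remedy for counting only transferred cycles. It removes confounding by hospital, not selection of women after randomisation.

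**Conclusion.** The point holds as a minor efficiency and specification gap. The plan is silent on hospital; it does not choose an unadjusted analysis. No conclusion of the trial is threatened.

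The size and power figures rest on between-hospital SDs that the documents do not give, a two-sided test and 851 analysed per arm. The larger power gains also need 36% as the intervention rate. In the per-transferred-cycle analysis the direction depends on whether transfer rates differ by arm and track hospital success.

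The case for acting does not rest on power alone: stating the model fixes which odds ratio is reported, and makes the intention-to-treat and per-protocol results comparable.

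**What to change.** In Statistical analysis method, item 3:
- Pre-specify hospital (14 levels) as a term in the model for live birth and for the common secondary outcomes: biochemical, clinical and ongoing pregnancy. Use the same model in the intention-to-treat and per-protocol analyses of item 5.
- Report a hospital-standardised risk difference with 95% CI beside the hospital-adjusted odds ratio.
- For rare binary safety outcomes, use a Mantel-Haenszel analysis stratified by hospital, or leave them unadjusted, and align item 4 with that choice.

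The cost is a few lines of text and an odds ratio that must be described as conditional on hospital. Hospital is already recorded for randomisation, so no new data are needed. If hospitals do not differ, almost nothing is lost on the primary outcome: simulated power at 30% v 36% was 74.5% without the term and 74.8% with it.

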Patients will receive luteal phase support with intramuscular progesterone (60mg/day) since the day of oocyte retrieval. On day 3 after oocyte retrieval, two top quality cleavage-stage embryos will be transferred via a catheter under transabdominal ultrasound guidance. The patients will lie in bed for 15 minutes after the procedure. After embryo transfer, 8% progesterone sustained-releasing vaginal gel (Crinone®, Merck, Switzerland) 90mg and dydrogesterone (Duphaston®, AbbottBiologicals, Netherlands) 20mg every day will be used as luteal phase support, continuing for at least 2 weeks. For those who get pregnancy, luteal phase support will be continued to 10 weeks of gestation. The dosage adjustment will be determined by physicians of each study site according to their personal experience.

Pregnancy evaluation and follow-up

All the information will be recorded in our follow-up forms designed specifically for each follow-up visit.

1. *Biochemical determination:* 14 ± 4 days after embryo transfer, serum β -hCG will be tested to determine pregnancy.
2. *Clinical pregnancy determination:* 28 ± 4 days after embryo transfer, a transvaginal ultrasound scan will be performed to confirm the presence of fetal sac, yolk sac and fetal heart.
3. *Ongoing pregnancy determination:* A transvaginal ultrasound scan will be performed at 10-12 weeks of gestation to confirm ongoing pregnancy. The presence of first-trimester pregnancy complications (e.g. OHSS, ectopic pregnancy, miscarriage etc.) will be registered according to the participant's medical record and a telephone follow-up.
4. *28 weeks of gestation:* A telephone follow-up will be conducted to collect the information regarding the second-trimester complications, e.g. pre-eclampsia, gestational diabetes,

prenatal diagnosis, miscarriage, etc.

5. 37 weeks of gestation: A telephone follow-up will be conducted to collect the information regarding the third-trimester complications, e.g. pre-eclampsia, gestational diabetes, preterm birth, etc.
6. *Delivery information:* A telephone follow-up will be made to collect delivery information including gestational age, delivery mode, delivery complications and infant information such as birth weight, any birth defect, etc.
7. *Postpartum information:* Postpartum information includes complications of both the mother and the infant, which will be collected 6 weeks after delivery.

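### Implantation rate and birth weight have no stated unit, and the plan names no method for two embryos or twins from one woman

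*Combined protocol and SAP*

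**What the plan says.** All references are to the combined protocol and SAP.

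- **Embryos per woman.** Trigger and oocyte retrieval, item 3: "Two top-quality Day 3 cleavage embryos will be transferred 72h after retrieval". The section on embryo transfer and luteal phase support repeats the number.
- **Effectiveness endpoints.** Secondary outcomes: "Secondary effectiveness endpoints will include implantation rate, biochemical pregnancy, clinical pregnancy and ongoing pregnancy". The three pregnancy endpoints are then defined at the level of the pregnancy; clinical pregnancy, for example, "is defined as the presence of an intrauterine gestational sac" at the 28-day scan. Implantation rate gets no numerator, denominator or unit. The only hint is in the Background, which attaches the word embryo to the rate when describing the proposed mechanism.
- **Infant endpoints.** The safety endpoints include "neonatal birth weight and adverse fetal outcomes", with no unit. Delivery follow-up collects "infant information such as birth weight, any birth defect, etc".
- **Analysis.** Statistical analysis method, item 3: "Between-group differences for categorical and continuous outcome variables will be assessed by logistic regression and linear regression, respectively". Item 4: "Adverse events and reaction will be listed and analyzed using the chi-square test". Neither item mentions clustered or robust standard errors, GEE, a mixed model, a per-woman summary or a rule for multiple births.

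**The concern.** Two embryos in one transfer share the parents, the stimulation cycle and the uterus, and twins share a pregnancy. Their outcomes are unlikely to be independent. Logistic and linear regression with their usual standard errors treat every record as independent. Applied to one row per embryo or per infant, they count more information than the trial holds when the correlation is positive.

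This affects one of the four secondary effectiveness endpoints and one of the safety endpoints. Implantation carries some weight, because the Background offers better endometrial receptivity and implantation as the reason the new protocol should work. A falsely significant result there would look like support for the mechanism. Leaving the unit open also lets it be chosen after the data are seen, in a trial whose physicians, nurses and embryologists know the allocation.

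**Working it through.** The plan gives no figure of its own for these endpoints, so there is none to reproduce. Its sample size concerns the primary outcome only.

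**Inputs from the documents:** two embryos per woman; 851 women per group before drop-out; planning live birth rates of about 30% and 40%.

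**Assumed inputs, none of them in the documents:** correlation between two embryos r = 0 to 0.3; within-pair correlation of twin birth weights ICC = 0.5 to 0.7; twin–singleton gap g = 0 to 1.5 SD.

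**1. Implantation analysed per embryo.** With two embryos per woman the design effect is DE = 1 + r. The usual standard error is too small by 1 − 1/√DE. The actual rejection rate of a nominal 5% test is 2 × (1 − Φ(1.96/√DE)).

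| r | DE | SE too small by | Rejection rate | Coverage of 95% interval |
|---|---|---|---|---|
| 0 | 1.0 | 0% | 5.0% | 95.0% |
| 0.1 | 1.1 | 4.7% | 6.2% | 93.8% |
| 0.2 | 1.2 | 8.7% | 7.4% | 92.6% |
| 0.3 | 1.3 | 12.3% | 8.6% | 91.4% |

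Simulation with no treatment effect (851 women per arm, 200,000 runs per setting) gave 5.0% at r = 0 and 6.2–8.6% at r = 0.1–0.3 for the unadjusted test. Standard errors clustered by woman gave 5.0–5.1%.

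**2. The same endpoint as one proportion per woman.** Each woman's value (sacs divided by embryos) is 0, 0.5 or 1. With two embryos each, its mean equals the per-embryo rate. Comparing these values by linear regression, one record per woman, gave 5.0–5.1% in simulation.

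**3. Twin share of deliveries, t.** Let p be the chance that one embryo leads to a live birth. Then P(both) = p² + r·p(1 − p). Solve 2p − P(both) = live birth rate, and t = P(both) / live birth rate.

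| Live birth rate | r = 0 | r = 0.1 | r = 0.2 | r = 0.3 |
|---|---|---|---|---|
| 30% | 8.9% | 14.6% | 20.8% | 27.7% |
| 40% | 12.7% | 18.6% | 25.0% | 32.0% |

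The range carried forward is 9–32%.

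**4. Birth weight analysed per infant.** With w = 2t/(1 + t), the share of infants who are twins:

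DE = {[(1 − t)(1 + (wg)²) + t(2(1 + ICC) + 4((1 − w)g)²)] / (1 + t)} / {1 + w(1 − w)g²}

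- Lowest corner, t = 0.089, ICC = 0.5, g = 0: DE = (0.911 + 0.089 × 3)/1.089 = 1.082, rejection rate 5.9%.
- t = 0.32, ICC = 0.7, g = 0: DE = (0.68 + 0.32 × 3.4)/1.32 = 1.339, rejection rate 9.0%.
- Highest corner, t = 0.32, ICC = 0.7, g = 1.5: w = 0.64/1.32 = 0.485 and DE = 1.403, rejection rate 9.8%.

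Coverage of a nominal 95% interval therefore runs from 94.1% down to 90.2%. Simulation with 300 deliveries per arm (about 851 × 0.35; 40,000 runs per setting) gave 6.1% at the first corner, 9.1% at the second and 9.6% at the third. Clustered standard errors gave 5.0–5.3% in the settings simulated.

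**The case against.** The strongest reply is that the plan under-specifies the analysis and does not prescribe a wrong one. Item 3 names the models and is silent on the variance estimator. Regression with clustered standard errors is still logistic or linear regression, and a per-woman proportion analysed by linear regression already fits the text and is valid. **This stands.** A reader might infer that the plan commits to treating embryos as independent; the documents do not say so. The fault is conditional on how the open choice is made.

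A reader might also infer that implantation must be meant per embryo, because a per-woman version would merely repeat clinical pregnancy. That is true only of a yes/no version. The proportion 0, 0.5 or 1 separates one sac from two and does not duplicate it. The Background wording points to an embryo-based rate but does not settle the method.

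Two further inferences go too far. The first is that narrow intervals would lead the trial to rule out a harm wrongly: the documents contain no safety margin or harm-exclusion rule. The second is that the chi-square test in item 4 would be misapplied to birth weight: birth weight is continuous, so item 3 is the relevant text.

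The birth-weight range does rest on three stacked assumptions, and a per-delivery summary would change it. Single-embryo transfers would also shrink the implantation figures slightly: if 20% of women had one embryo (assumed), the mean-weighted cluster size is 3.4/1.8 and the range becomes 6.0–8.2%. What the reply does not remove is that neither the unit nor any handling of pairs is stated, and that the most direct use of the named models on embryo or infant rows is the faulty one.

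**Conclusion.** The point holds in conditional form and should be fixed before the data are analysed. Implantation rate and birth weight have no stated unit, and nothing in the plan deals with two embryos or twins from one woman. If the named models are run on embryo or infant records with their usual standard errors, and the within-woman correlation is positive, intervals are too narrow. For implantation the rejection rate is 6.2–8.6% at an assumed correlation of 0.1–0.3. For birth weight it is about 6–10% under the assumptions listed. A per-woman analysis of implantation, or zero correlation, removes the fault for that endpoint.

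For adverse fetal outcomes a per-woman count is just as plausible, so the gap there is only the unstated unit.

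The sample size is unaffected. So is the primary outcome, which counts any viable infant per transferred cycle, provided only the fresh transfer enters. Methods/Design indicates this, although the outcome definition speaks of all transferred cycles and frozen–thawed cycles are also followed.

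**What to change.** - **Secondary outcomes.** Define implantation rate as gestational sacs divided by embryos transferred. Count the sacs at the scan already planned 28 ± 4 days after transfer, where "a transvaginal ultrasound scan will be performed to confirm the presence of fetal sac, yolk sac and fetal heart".
- **Item 3, implantation.** Choose one: a single proportion per woman, compared by linear regression with robust standard errors; or per-embryo regression with standard errors clustered by woman (GEE with an independence working correlation). With two embryos per woman both give the same rate.
- **Item 3, birth weight.** Analyse per infant with standard errors clustered by woman. The independence working correlation keeps the per-infant average as the target; an exchangeable one would weight twins differently. Report the twin rate by arm, and show birth weight by plurality descriptively only, because plurality arises after randomisation.
- **Adverse fetal outcomes.** State the unit. If it is the woman with any affected infant, keep the stated test; if it is the infant, cluster by woman.

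**Cost.** One definition, a few sentences of analysis text, a sac-count field on the scan form if it is absent, and a little more analysis work. No extra visit, scan or participant is needed. Implantation intervals widen by about 5–14% at correlations of 0.1–0.3 (√1.1 = 1.05, √1.3 = 1.14) compared with the unadjusted per-embryo analysis.
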